7. COUNTRIES INVOLVED

The survey will be conducted among healthcare professionals mainly from the eight European countries represented in the SERENITY consortium:

- Denmark
- France
- Germany
- Italy
- The Netherlands
- Poland
- Spain
- United Kingdom

Due to promotion of the project via international networks and social media (s. section 10), we also expect participants from other countries and regions. Depending on the number or proportion of participants from outside Europe, these will be evaluated separately.

8. (TARGETED) NUMBER OF SUBJECTS

The study aims to generate data from a total of at least 800 healthcare professionals (i.e., either 100 each from the countries listed in section 7 or corresponding participant numbers from additional countries) and up to 2400 anonymised patients, considering that each healthcare professional will be asked to describe actual decisions and anonymous data obtained from medical charts in one to three consecutive patients meeting the definitions below at the time of consideration.

9. SAMPLE SIZE CONSIDERATIONS

In view of the FMR design, there is no formal predetermined sample size. In principle, a successful FMR should include a large sample size for reliable and generalizable conclusions.³

For DCE, the required sample size (N) depends on the number of choice tasks (t), the number of alternatives (a), and the number of analysis cells (c) according to the following equation: $N > 500c/(txa)$. Where DCE studies usually require only 100 responses, the minimum sample size to show that deprescribing ATT in a certain setting is preferred over continuing the ATT with a statistical power β of 80% and a 2-sided significance level α of 0.05 is 190. This is well below the planned number of 800 observations.⁴

We will monitor the number of preregistered participants and adjust the recruitment plan based on the actual accrual.

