10. DESCRIPTION OF STUDY PROCEDURES

The study will be divided into three phases: the recruitment phase, the FMR-phase and the data analysis phase.

In the **recruitment phase**, the national coordinators of the project group will advertise the study through traditional professional networks as well as their social media channels. Information about the study will be distributed via personal communication, relevant scientific organisations and journals, and via social media. The healthcare professionals of interest will be invited to pre-register for study participation so they can be assigned a unique link to the electronic case report forms (eCRF). During the preregistration, characteristics of the pre-registrants will be checked (i.e., sex, age, profession, years of experience, the country where they are practicing, and the number of cancer patients in palliative care whom they care for on a yearly basis).

In the **FMR phase**, all preregistered participants will be asked simultaneously to complete the survey using the *Castor electronic data capture platform* within seven days.

The survey will be divided into the following sections:

- a) **General questions** regarding end-of-life care (e.g., "When do you consider a patient in end-of-life care?") and (de)prescription of antithrombotic medication to cancer patients during end-of-life care (e.g., "Have you ever considered deprescribing antithrombotic medicine?").
- b) A sequence of **choice scenarios** i.e., hypothetical scenarios that vary with regard to several characteristics (**attributes**; e.g., bleeding risk, thrombotic risk). Attributes will be further specified by varying choice levels (**attribute levels**; e.g., low or high bleeding risk), which are considered relevant for the decision on continuation or stopping antithrombotic medication in the patient population studied. In accordance with the discrete choice experiment (DCE) methodology, participants will be asked to select the healthcare intervention (i.e., either continuation or discontinuation of the antithrombotic therapy) that in their opinion would benefit the patient the most within each choice set.
- c) Participants will be asked to share **actual case decisions** they made in a maximum of three consecutive cases involving patients with active cancer, who were considered to receive end-of-life care. Fully anonymised data of the patients (sex, age category, primary tumour, tumour

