13. STATISTICAL ANALYSIS

The main analysis of the FMR will be descriptive. Results will be presented for all predefined subgroups and with corresponding 95% confidence intervals. Responses to the DCE will be used to generate preference coefficients for each level of each attribute using random parameters logit regressions, where preference weights represent the relative contribution of the attribute level to the value that participants assigned to an alternative management decision.

The attribute-level coefficients will be expressed as mean preference weights and standard deviations of the mean preference weights, each with appropriate 95% confidence interval. The relative importance of each attribute will be expressed using the within-attribute difference in preference weights as a percentage of the total difference in preference weights across all attributes. For the coefficients, the algebraic sign (positive or negative) of a coefficient reflects whether respondents feel positive or negative with regard to deprescribing. The value of a coefficient indicates the relative importance of the corresponding attribute. The statistical significance of a coefficient ($p \leq 0.05$) indicates that the respondents underline the importance of the attribute within the options in the DCE.

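### Section 9 claims power to show that deprescribing is preferred in a given setting, but Section 13 specifies no setting-level estimate of stopping versus continuing and reads coefficient signs as if they supplied one

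*Combined protocol and SAP*

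**What the plan says.** Section 9 (Sample size considerations) describes 190 as "the minimum sample size to show that deprescribing ATT in a certain setting is preferred over continuing the ATT", at 80% power and a "2-sided significance level α of 0.05". It sets 190 against the planned total of 800. It names no setting and states no assumed effect. It also gives a rule of thumb, N > 500c/(t × a), without values for c, t or a.

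Section 10 defines the response in each choice task as "either continuation or discontinuation of the antithrombotic therapy". In the Section 15.3 examples, the attributes describe the patient and the drug: performance status, thrombotic risk, bleeding risk and type of medication.

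Section 13 (Statistical analysis) states: "Responses to the DCE will be used to generate preference coefficients for each level of each attribute using random parameters logit regressions". The listed outputs are mean preference weights, their standard deviations, 95% confidence intervals and the relative importance of each attribute. The sign of a coefficient is read as respondents' feeling for or against deprescribing, and p ≤ 0.05 as showing that the attribute matters. No constant, predicted choice share or scenario-level contrast is mentioned.

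**The concern.** The only power statement in the plan concerns which option is preferred in a setting. The planned outputs concern how much each attribute level moves the choice. These are different quantities, and the second does not determine the first.

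The sign rule makes this more than a missing detail. A report that follows Section 13 literally could say that professionals favour deprescribing at high bleeding risk because that coefficient is positive, when most respondents would still continue treatment in every such scenario. Section 3 calls the study a first step towards a clinical decision tool, so that misreading could be carried forward.

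**Working it through.** **1. Can 190 be reproduced?** Not from the plan's own inputs, because no effect is given. It can only be back-solved. For one proportion against p0 = 0.50, with z = 1.96 and 0.8416 and an assumed share p = 0.60:

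- Null and alternative variances: [(1.96 × 0.5 + 0.8416 × √0.24) / 0.10]² = 193.8, so 194.
- Alternative variance only: (1.96 + 0.8416)² × 0.24 / 0.01 = 188.4, so 189.
- Null variance only: (1.96 + 0.8416)² × 0.25 / 0.01 = 196.2, so 197.

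So 60% against 50% is compatible with 190, but other routes come as close:

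- A one-sided test of 59% against 50% gives 185 to 191, depending on the variance used.
- Two-group totals are 194 (40% against 60%) and 186 (50% against 70%).
- The rule of thumb gives 500 × 3 / (4 × 2) = 187.5, and also 500 × 6 / (8 × 2) = 187.5.

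The figure is undocumented. It is not shown to be wrong.

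**2. Do the Section 13 outputs answer the Section 9 question?** In a two-option logit whose attributes describe the case, the share choosing to stop is 1 / (1 + exp(−(α + β))). Here α is the discontinue-versus-continue constant at the reference levels and β is the coefficient of the level of interest. Take β = +1 for high bleeding risk. This value and both constants are assumed, and variation between respondents is ignored.

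| Constant α | Share stopping, reference level | Share stopping, high bleeding risk |
|---|---|---|
| 0 | 1/(1 + e⁰) = 50% | 1/(1 + e⁻¹) = 73% |
| −2 | 1/(1 + e²) = 12% | 1/(1 + e¹) = 27% |

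The coefficient and its sign are the same in both rows. The preferred option at high bleeding risk is stopping in the first and continuing in the second. Only α separates them, and Section 13 does not report it.

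Coding shows the same thing. If low bleeding risk is modelled against high, the coefficient becomes −1 with no change in the data. The sign rule would then have the same respondents feeling negative about deprescribing.

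**3. Multiplicity, if scenarios are compared with 50%.** Section 15.3 shows 8 blocks of 3 example scenarios, 24 in all. Testing each at 0.05 would give 24 × 0.05 = 1.2 expected false positives if every true share were 50%.

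**4. Precision, if DCE results were shown by country.** Section 8 targets "either 100 each from the countries listed in section 7" or equivalent numbers from elsewhere. The 95% half-width for a share near 50%, with one choice per respondent, is 1.96 × √(0.25/n): 9.8 points at n = 100 and 3.5 points at n = 800. Approximate power at n = 100 is Φ[((p − 0.5)√100 − 1.96 × 0.5) / √(p(1 − p))]:

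| Assumed true share p | Power at n = 100 |
|---|---|
| 55% | 17% |
| 60% | 52% |
| 65% | 86% |
| 70% | 99% |

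**The case against.** The best reply is that the logit already models stopping against continuing, because the response is binary. Section 13 lists outputs rather than the full model, so the absence of a constant is inferred from silence. Stopping shares per scenario can be obtained from the data that will be collected. The second objective in Section 4 is about the factors behind decisions, and attribute-level coefficients serve that objective.

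Much of this stands. A reader might infer that the study cannot say where professionals prefer stopping. That goes too far: the data would allow it, and the plan simply does not commit to the estimate. The reply does not rescue the sign rule, which assigns to coefficients a meaning they do not carry. Nor does it link the Section 9 power claim to any named output.

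A reader might also infer that 100 per country falls short of 190. The documents do not support that as a defect. Section 9 sets 190 against the pooled 800, which is more than four times larger, and no country-level DCE test is planned. The sentence "Results will be presented for all predefined subgroups" follows directly on the descriptive flash mob analysis, promises confidence intervals, and neither lists the subgroups nor names country. Section 8 lets numbers from additional countries replace the 100. Section 9 itself says that such experiments usually need only 100 responses, and its rule of thumb gives 500 × 3 / (8 × 2) = 93.8 for an assumed c = 3, t = 8 and a = 2.

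Lastly, 60:40 should not be treated as the sponsor's assumption, since several other readings also lead to about 190.

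**Conclusion.** The point holds as a mismatch between Sections 9 and 13, together with a sign interpretation that can mislead. The analysis as written does not specify the stop-versus-continue estimate for which power is claimed, and a coefficient's sign cannot stand in for it. The 73% against 27% contrast rests on assumed coefficients. It shows that the answer can reverse, not that it will in this study.

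The missing effect behind 190 is, taken alone, a documentation gap. It does not show that the sample is too small, and no change in sample size follows. The country-level figures matter only if DCE results are reported by country. They depend on the assumed share, which is why a range is given.

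**What to change.** **Section 13**

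- Include a discontinue-versus-continue constant in the random parameters logit and report it.
- For each scenario, or a small set named in advance, report the predicted share choosing discontinuation, averaged over the random-parameter distribution. Give a 95% confidence interval that accounts for repeated choices by the same respondent.
- Name the scenario or scenarios formally compared with 50% and treat the rest as descriptive.
- Reword the sign rule: a coefficient shows a shift towards or away from deprescribing relative to the reference coding, not a preference for it.

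**Section 9**

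- The sponsor states its own assumed effect and setting behind 190. A share of about 60% against 50% is one compatible reading, to be confirmed or replaced.
- State that the power claim applies to the pooled sample.
- If DCE results are shown by country, label them descriptive and give the precision of about ±10 percentage points at 100 respondents.

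The cost is one extra output table, some rewording and a slightly narrower power claim. No extra respondents or survey questions are needed.

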10. DESCRIPTION OF STUDY PROCEDURES

The study will be divided into three phases: the recruitment phase, the FMR-phase and the data analysis phase.

In the **recruitment phase**, the national coordinators of the project group will advertise the study through traditional professional networks as well as their social media channels. Information about the study will be distributed via personal communication, relevant scientific organisations and journals, and via social media. The healthcare professionals of interest will be invited to pre-register for study participation so they can be assigned a unique link to the electronic case report forms (eCRF). During the preregistration, characteristics of the pre-registrants will be checked (i.e., sex, age, profession, years of experience, the country where they are practicing, and the number of cancer patients in palliative care whom they care for on a yearly basis).

In the **FMR phase**, all preregistered participants will be asked simultaneously to complete the survey using the *Castor electronic data capture platform* within seven days.

The survey will be divided into the following sections:

- a) **General questions** regarding end-of-life care (e.g., "When do you consider a patient in end-of-life care?") and (de)prescription of antithrombotic medication to cancer patients during end-of-life care (e.g., "Have you ever considered deprescribing antithrombotic medicine?").
- b) A sequence of **choice scenarios** i.e., hypothetical scenarios that vary with regard to several characteristics (**attributes**; e.g., bleeding risk, thrombotic risk). Attributes will be further specified by varying choice levels (**attribute levels**; e.g., low or high bleeding risk), which are considered relevant for the decision on continuation or stopping antithrombotic medication in the patient population studied. In accordance with the discrete choice experiment (DCE) methodology, participants will be asked to select the healthcare intervention (i.e., either continuation or discontinuation of the antithrombotic therapy) that in their opinion would benefit the patient the most within each choice set.
- c) Participants will be asked to share **actual case decisions** they made in a maximum of three consecutive cases involving patients with active cancer, who were considered to receive end-of-life care. Fully anonymised data of the patients (sex, age category, primary tumour, tumour

stage, time point in the course of the disease when the conversation about discontinuation of ATT took place, type and indication of ATT) will be collected via multiple-choice questions.

11. REGULATORY AND LEGAL REQUIREMENTS

As confirmed by the responsible ethics committee, due to the non-interventional nature of this study and since no personal data of patients will be recorded or processed, professional advice and/or submission of this protocol to the ethics committee before commencement of the survey is not required.

Data privacy of participating healthcare professionals will be taken into account in accordance with the European General Data Protection Regulation (GDPR). With the exception of the e-mail addresses of survey participants for the purpose of forwarding the survey link and information on survey launch and completion, no personal data will be stored or processed. As detailed in the information for prospective participants, participants implicitly consent to the use of their e-mail addresses for said purposes by pre-registering.

Data on patients will be sufficiently coarsened such that no identification will be possible. As an additional security measure, this part of the survey will be exported and analyzed separately from the other two sections (s. section 9 above).

12. STUDY DURATION AND TIMELINES

The total duration of this study is expected to be twelve months.

The recruitment phase, in which the healthcare professionals will be asked to preregister for study participation, will start in March 2023. One week before the study is open for data entry, preregistered healthcare professionals will receive an email with details on the study launch. Data collection (i.e., the FMR phase) will start in the first week of May 2023 and take seven days. Data analysis and publication of results will be conducted from June to October 2023.

13. STATISTICAL ANALYSIS

The main analysis of the FMR will be descriptive. Results will be presented for all predefined subgroups and with corresponding 95% confidence intervals. Responses to the DCE will be used to generate preference coefficients for each level of each attribute using random parameters logit regressions, where preference weights represent the relative contribution of the attribute level to the value that participants assigned to an alternative management decision.

The attribute-level coefficients will be expressed as mean preference weights and standard deviations of the mean preference weights, each with appropriate 95% confidence interval. The relative importance of each attribute will be expressed using the within-attribute difference in preference weights as a percentage of the total difference in preference weights across all attributes. For the coefficients, the algebraic sign (positive or negative) of a coefficient reflects whether respondents feel positive or negative with regard to deprescribing. The value of a coefficient indicates the relative importance of the corresponding attribute. The statistical significance of a coefficient ($p \leq 0.05$) indicates that the respondents underline the importance of the attribute within the options in the DCE.

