15. APPENDICES

15.1 Survey: Questions for pre-registration

1. Please select your country (*Denmark; France; Germany; Italy; The Netherlands; Poland; Spain; United Kingdom*)
2. Please select your age category (*25-34; 35-44; 45-54; 55-64; 65 or older*)
3. Please select your sex (*male; female; other*)
4. Please select your profession (*general practitioner; palliative care specialist; nursing home physician; geriatrist; vascular medicine specialist; oncologist; haematologist; pulmonologist; cardiologist; neurologists; vascular surgeon*)
5. Please select the professional experience group that matches your years of experience (*< 5 years; 5-10 years; 11-15 years; 16-20 years; 21 or more*)
6. Please provide an estimate on the number of patients you see/treat with active cancer each year, who are considered to be in end-of-life care.
This number is important for the upcoming data collection.

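### 15.1 item 1 offers only the eight consortium countries, so respondents from elsewhere can be neither counted nor separated as Sections 7 and 8 foresee; a minor second gap is the interval method for one to three cases per professional

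*Combined protocol and SAP*

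**What the plan says.** **Country.** Section 7 names eight consortium countries and then says "we also expect participants from other countries and regions". It adds: "Depending on the number or proportion of participants from outside Europe, these will be evaluated separately". Section 8 sets the target at 100 professionals from each of the eight "or corresponding participant numbers from additional countries". Section 10 says that country of practice is checked at pre-registration. The form for this is 15.1, whose item 1 offers "Denmark; France; Germany; Italy; The Netherlands; Poland; Spain; United Kingdom" and nothing else. None of 15.2, 15.3 or 15.4 asks for country. Objective 1 in Section 4 concerns European practice.

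**Cases and intervals.** Section 8 states that "each healthcare professional will be asked to describe actual decisions and anonymous data obtained from medical charts in one to three consecutive patients", and 15.4 repeats the range of one to three. Section 13 calls the FMR analysis descriptive and says "Results will be presented for all predefined subgroups and with corresponding 95% confidence intervals". It names no interval method or unit of analysis for the case data; the random parameters logit model is specified for the DCE only. Section 10 gives each pre-registrant a unique eCRF link. Section 11 says of the case part that "this part of the survey will be exported and analyzed separately from the other two sections", and also that "Data on patients will be sufficiently coarsened such that no identification will be possible". It is silent on whether a respondent number goes with the case file.

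**The concern.** The plan expects respondents from beyond the eight countries, counts some of them toward its target, and foresees treating one group of them differently in the analysis. The variable needed for all three is limited to the eight countries. A respondent in, say, another European state and one outside Europe look the same on this form, because neither has an answer to give. At stake are the separate evaluation in Section 7, the accounting in Section 8, and the claim that objective 1 describes European practice. All three survey parts are affected.

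The second matter is smaller. Cases reported by one professional share a decision-maker, so their outcomes may be correlated. If they are, intervals computed as though all cases were independent would be too narrow for the data on actual decisions.

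**Working it through.** **1. Country: the passages side by side**

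| Task in the plan | Information needed | Available from 15.1 item 1? |
|---|---|---|
| Separate evaluation of respondents outside Europe (Section 7) | Europe versus outside Europe | No |
| Counting additional countries toward 800 (Section 8) | Name of each additional country | No |
| European practice (objective 1) | Europe versus outside Europe | No, for anyone outside the eight |

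A respondent from elsewhere can fail to register, leave the item blank, or choose a wrong country. In the first case they are lost. In the second they are visibly outside the eight, but Europe and non-Europe are not told apart. In the third they are mislabelled. None of these permits the three tasks.

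Illustration only, with both inputs assumed: if outside-Europe respondents are pooled with the rest, the pooled proportion shifts from the European one by share × difference. With a share of 5%/10%/20% and a 20-point difference in deprescribing, the shift is 0.05 × 20 = 1, 0.10 × 20 = 2 and 0.20 × 20 = 4 points.

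**2. Case-level intervals**

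The plan's own figures reproduce: 8 × 100 = 800 professionals and 800 × 3 = 2400 cases.

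Inputs: 800 professionals with one to three cases each (Section 8). Assumed: proportion 0.5 and ICC 0.1/0.3/0.5, since the documents give no ICC.

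Formulas:
- Design effect: DEFF = 1 + (m̃ − 1) × ICC, with m̃ = Σm²/Σm.
- Half-width: 1.96 × √(0.25 × DEFF / N).
- True coverage of a nominal 95% interval that ignores clustering: 2Φ(1.96/√DEFF) − 1.

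Three cases each has m̃ = 3. Equal thirds with one, two and three cases has m̃ = (1 + 4 + 9)/(1 + 2 + 3) = 14/6 = 2.33.

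| | N | DEFF | Half-width ignoring clustering | Half-width allowing for it | Coverage if ignored |
|---|---|---|---|---|---|
| Three each | 2400 | 1.20/1.60/2.00 | 2.00 | 2.19/2.53/2.83 | 92.6%/87.9%/83.4% |
| Equal thirds | 1600 | 1.13/1.40/1.67 | 2.45 | 2.61/2.90/3.16 | 93.4%/90.2%/87.1% |
| One each | 800 | 1 | 3.46 | 3.46 | 95% |

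The largest widening in this range is 2.83 − 2.00 = 0.83 points.

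*Respondent-level subgroup.* For 100 professionals with three cases each (N = 300), the half-width goes from 5.66 to 6.20/7.16/8.00. The ratio is the same as overall: 8.00/5.66 = 2.83/2.00 = 1.41.

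*Patient-level subgroup.* Assume each of a professional's three cases falls in the subgroup independently with probability q. Then m̃ = [3q(1 − q) + 9q²]/(3q) = 1 + 2q, so DEFF = 1 + 2q × ICC. At q = 0.25 this is 1.05/1.15/1.25, and coverage is about 94%/93%/92%.

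*Simulation check.* Beta-binomial data, 4000 runs, 800 professionals with three cases each: intervals ignoring clustering covered 91.8%/86.7%/82.7%, and cluster-robust intervals 94.8%/94.2%/95.2%.

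**The case against.** On country, one can reply that mixing of regions is not inevitable. The form might simply keep others out, or a blank would mark them as outside the eight. That is fair: a reader might infer that European and non-European answers will certainly be pooled, and the documents do not show this. It does not rescue the plan, because exclusion contradicts Sections 7 and 8, and a blank cannot distinguish Europe from elsewhere. Nor is 15.1 presented as a set of examples, as 15.2.1 and 15.3 are.

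On clustering, most of the reply stands. A reader might infer that Section 13 treats cases as independent; it does not say so, it only names no method. Under-coverage needs a positive ICC, which the documents do not give, and the 83% figure rests on the top assumed value. A reader might also infer that separate export strips the respondent key. Section 11 does not say that, and the unique link in Section 10 ties cases to a respondent at capture. Nor is the problem proportionally worse in subgroups: the ratio is unchanged in respondent-level subgroups and smaller in patient-level ones. By-country case results cannot carry the argument either, since Section 13 does not list the subgroups and the 15.4 items hold no country field.

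Finally, the general questions are answered once per professional and are untouched by clustering. What remains is a missing detail that is easy to supply.

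**Conclusion.** The country list is wrong as written. Sections 7 and 8 require information that 15.1 item 1 cannot record and that no later item collects. This conclusion rests on the text alone and needs no assumption. The number of respondents affected, and any resulting shift in estimates, cannot be known from the documents.

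The interval method is a minor, secondary point. It matters only if professionals report more than one case and the within-professional correlation is positive. Within the assumed ICC range the overall loss of precision is at most about 0.8 percentage points, although coverage could fall to about 83% in the most adverse setting examined. The FMR analysis is descriptive and has no formal sample size (Section 9), so no test or sample size depends on these intervals.

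**What to change.** 1. **15.1 item 1:** add 'other country (please specify)' and derive a Europe/outside-Europe indicator from it. A single lumped 'other European country' option would not be enough, because Section 8 needs numbers for each additional country.
2. **Case file:** carry only the two-level indicator into it, or apply the indicator as a filter before export. Choose between them by a small-cell check against the Section 11 statement on identification.
3. **Section 13:** state that case-level 95% intervals take the respondent as cluster (for example cluster-robust), and report the number of cases per respondent.
4. **Section 11:** keep the case file separate, but export it with a random respondent number that is used only in that file and is not tied to the e-mail address. Include the linking of up to three patients in the same small-cell check.

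The cost is one answer option, a derived variable, a few sentences, somewhat wider intervals and the privacy check. That check must count patient records. From 15.4, age × cancer type × stage gives 3 × 11 × 4 = 132 cells, or 2400/132 ≈ 18 patients per cell on average. An outside-Europe group of 5% (assumed; 0.05 × 2400 = 120 cases) would average 120/132 ≈ 0.9 per cell, which is why the filter option is there. These averages suppose evenly filled cells and do not themselves measure disclosure risk.

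### Section 13 puts no interval on the relative-importance percentages, a range-based share that is biased upward for weak attributes and needs a joint test beside it

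*Combined protocol and SAP*

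**What the plan says.** Section 13 of the combined protocol and SAP fits the DCE responses "using random parameters logit regressions". It reports "mean preference weights and standard deviations of the mean preference weights, each with appropriate 95% confidence interval". The next sentence turns to attributes: "The relative importance of each attribute will be expressed using the within-attribute difference in preference weights", taken "as a percentage of the total difference in preference weights across all attributes". No interval, standard error, bootstrap or delta method is attached to this percentage there or elsewhere.

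The section's other interval promise, "Results will be presented for all predefined subgroups and with corresponding 95% confidence intervals", follows directly on the statement that the flash mob analysis is descriptive, so it belongs to that part of the study.

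Two further sentences bear on importance. One says "The value of a coefficient indicates the relative importance of the corresponding attribute", which is a second definition. The other says that p ≤ 0.05 for a coefficient "indicates that the respondents underline the importance of the attribute within the options in the DCE".

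**The concern.** The percentages are the only normalised measure in the plan that compares attributes with one another. The second objective (section 4) is to understand the factors behind deprescribing decisions, and section 3 presents the results as a first step towards a decision tool. Readers are likely to use the percentages to judge which factors weigh most.

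A share built from ranges has two properties that the plan does not mention. It is never below zero, so a factor with no effect still shows some importance. It also grows by chance with the number of levels. Without an interval, a small share cannot be told from noise on its own scale, and a gap between two shares cannot be judged at all.

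**Working it through.** **1. The measure.** For attribute k with level weights w, I read the within-attribute difference as R_k = max(w) − min(w), and the share as S_k = R_k / ΣR_j. Every R_k ≥ 0, so S_k ≥ 0 whatever the truth. Estimation error can only push the range of a null attribute upward from zero. This follows from the definition and needs no assumed effect sizes.

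**2. Number of levels.** The examples in section 15.3 have three two-level attributes (performance status, thrombotic risk, bleeding risk) and one three-level attribute (drug), giving 2 × 2 × 2 × 3 = 24 profiles. Take a balanced design with n observations, error SD σ and no true effects.
- Two levels: the difference of two level means has SD 2σ/√n. Its expected absolute value is √(2/π) × 2σ/√n = 1.60σ/√n.
- Three levels: each level mean has SD √3σ/√n. The expected range of three is (3/√π) × √3σ/√n = 2.93σ/√n.
- Ratio: 2.93/1.60 = 1.84.

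A null three-level attribute therefore starts with a chance range nearly twice that of a null two-level one.

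**3. The plan's own figure.** Section 9 gives 190 as the minimum sample for showing that deprescribing is preferred. It states no effect size and no values for tasks, alternatives or cells, so 190 cannot be derived from its inputs. An undisclosed 60% against 50% would come close: (1.960 + 0.842)² × 0.6 × 0.4 / 0.1² gives 189, and other variance choices give 194 or 197. In any case 190 concerns a preference, not the precision of a share.

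**4. Size, under assumptions.** The documents give no weights, between-respondent variation or number of tasks, so all of these are assumed. I simulated 500 data sets per setting on the 24 example profiles, with a stop/continue choice and 8 or 24 tasks per respondent. Weights are effects-coded. Between-respondent SDs are 0.7 (intercept), 0.5 (two-level attributes) and 0.35 (drug). A pooled logit stands in for the random parameters model.

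*Scenario A*: thrombotic risk 0.5, bleeding risk 0.6, performance status and drug zero. True shares are 0.5/1.1 = 45.5%, 0.6/1.1 = 54.5%, 0 and 0. Cells give 8 tasks / 24 tasks.

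| N | Null drug, mean share % (2.5th-97.5th percentile) | Null performance status, mean share % | Top two swapped, % |
|---|---|---|---|
| 100 | 10.5 (2.3-20.8) / 6.7 (1.3-14.3) | 6.0 / 4.6 | 27.6 / 13.0 |
| 190 | 7.9 (1.5-17.4) / 4.8 (1.2-10.2) | 4.6 / 3.4 | 18.8 / 8.6 |
| 800 | 4.1 (0.8-8.7) / 2.5 (0.4-5.0) | 2.5 / 1.7 | 3.0 / 0.4 |

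The null drug attribute outranked the equally null performance status in 63-76% of replicates across the settings run, where an even comparison would give 50%.

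*Scenario B*, a near-tie: thrombotic risk 0.5, bleeding risk 0.55, performance status 0.1 (true share 0.1/1.15 = 8.7%), drug zero.

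| N | Top two swapped, % | Null drug ranked above performance status, % |
|---|---|---|
| 100 | 36.6 / 27.8 | 58.4 / 41.4 |
| 190 | 28.8 / 23.4 | 47.6 / 24.6 |
| 800 | 15.2 / 6.4 | 15.0 / 1.0 |

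**5. Sensitivity to the weights.** Across further assumed weights, the mean share of a null three-level attribute was about 2-8% at N = 800 and 5-18% at N = 100. Halving the two leading weights of scenario A moves the results to the upper part of these ranges, because the denominator shrinks while the noise does not.

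**6. What the coefficient intervals cover.** For a two-level attribute, R_k is a fixed multiple of the absolute value of one coefficient, so that coefficient's interval shows directly whether the effect is compatible with zero. For the drug attribute there are two free coefficients, and the plan tests them singly. For S_k itself, or for S_j − S_k, every coefficient and their covariances enter, and no reported quantity supplies the precision.

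**The case against.** The strongest reply is that the coefficients are the first-named DCE output and carry intervals and p-values, while the percentage is a descriptive by-product. Much of this stands, and it rules out several stronger readings.

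- A reader might infer that the percentages are the headline DCE result, or that the plan ranks attributes on them. Section 13 says neither, and the second objective does not ask which factor matters most.
- A reader might infer that a null factor would pass unnoticed. For two-level attributes it should not, as step 6 shows. Level-wise intervals also say something about the drug attribute, although a joint test is cleaner.
- A reader might infer that country or profession shares are planned. The subgroup sentence attaches to the flash mob analysis, and no subgroup DCE model is described. N = 100 is the per-country recruitment figure in section 8, not a planned DCE analysis set.
- A reader might assume that recruitment will fall short. Section 9 says that accrual will be monitored and recruitment adjusted.
- An interval on the share alone would not settle whether an attribute is null. Every resampled share is also non-negative, so a percentile interval for a null attribute can lie wholly above zero.

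The omission remains after all this. Nothing reported gives the precision of a share or of the difference between two shares, and no joint test covers the drug attribute.

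**Conclusion.** The point holds as a cheap improvement, not as a flaw that threatens the study. Two parts rest on the documents and the definition alone: the percentages have no interval, and a range-based share is non-negative and biased upward for weak attributes, more so with more levels.

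The size rests on assumed weights, heterogeneity and task counts, on example profiles that may not be the final design, and on a pooled-logit approximation. On that footing the effect at 800 is modest. A null attribute averages about 2-8%, and clear orderings are mostly stable. A near-tie of 0.50 against 0.55 is reversed in 6.4-15.2% of samples. At 190, the same near-tie is reversed in 23.4-28.8% of samples and the wider gap of scenario A in 8.6-18.8%. Groups of about 100 are worse still, should shares be reported for them.

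**What to change.** Add to section 13:

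> *Relative importance is reported with a 95% interval from a bootstrap resampling respondents (or simulation from the coefficient covariance matrix). Two attributes are described as differing in importance only if the interval for the difference in shares excludes zero. Whether an attribute has any effect is judged by a joint Wald or likelihood-ratio test of all its level coefficients, not by the interval of its share, which is bounded at zero.*

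Apply the same rule to any subgroup for which shares are shown. Also reconcile the range-based share with the sentence that reads a coefficient's value as relative importance, so that the plan has one definition.

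The cost is a few sentences and some computing time, since the random parameters model must be refitted for each bootstrap sample (simulation from the covariance matrix avoids this). No new data are needed. The downside is that some orderings will look less clear-cut. The interval also does not remove the upward bias from extra levels, so the number of levels should be shown beside each share.
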